BDI II for subjective ratings of depressive symptoms; 5) C-SSRS to assess suicidal ideation; 6) Medical history and vital signs; 7) Neuropsychological assessment to exclude HAD; 8) HIV plasma RNA viral load test; 9) Biological assessment: comprehensive immune, virologic and neuroendocrine measures, a complete blood count (CBC), and a comprehensive metabolic panel (CMP); and 10) Pregnancy test. These procedures may happen at our research offices, remotely via private video or telephone call, or on our Mobile Clinical Trials Unit (MCTU). The SCID-RV, HAM-D, and C-SSRS will be audio recorded for training purposes on a digital audio recorder or on Bluejeans. Subjects will also sign a release of information to allow us to communicate with their HIV primary care provider. The baseline assessment may be completed in one longer visit (8-10 hours) or two shorter visits (each 4-5 hours).

Randomization The 180 HIV-seropositive eligible and consenting depressed subjects will be randomized to 10 weeks of double blind therapy with either escitalopram or placebo. Study medication may be sent to participants via mail. All participants will concurrently begin CCBT. Stratification based on race, sex, and baseline depression symptom severity, will be incorporated to ensure an even distribution of more severely depressed subjects (i.e., those with HAM-D scores greater than or equal to 20) in each treatment condition. Neither the research nurse nor the study clinicians will be aware of the assigned treatment condition for each subject nor will any research staff having any clinical contact with the study participants be aware of the treatment assignment during each subjects participation in the study. Only the research pharmacist will be unblinded to the treatment condition during each subjects participation.

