inflammation in depressed HIV seropositive individuals. Hypothesis: SSRI is superior to placebo in decreasing biomarkers of inflammation (IL-6, CRP). Both MDD and HIV infection are associated with elevated levels of pro-inflammatory cytokines (for review see (7, 128-130). Although increased levels of many cytokines, inflammatory and oxidative stress markers were linked to either of those conditions extensive literature review show that IL-6 and CRP are two markers most consistently associated with both MDD and HIV infection. We

propose to use changes in those two markers as a primary outcome of our study. For example in our recent clinical trial with aprepitant, a compound with potential utility as a drug for depression and anti-inflammatory properties in HIV infected subjects, in non-depressed subjects we detected a decrease in plasma levels of IL-6 after 2 weeks of treatment within subjects ($p=0.02$) and between aprepitant and placebo ($p=0.02$) (131) (Figure 7). In addition to our primary variables (IL-6 and CRP) associated with inflammation, we will measure several other plasma markers of inflammation in HIV positive depressed subjects receiving SSRI or placebo (see C.4 Further Analyses).

Secondary Aim. Determine if improvement in depressive symptoms is associated with improvements in innate immunity and inflammation in HIV seropositive individuals.

Hypothesis: Reduced symptoms of depression after acute (10-week) treatment will correlate with increased

[figure not shown]

Figure 7. Changes in plasma levels of IL-6 in patients treated with aprepitant. IL-6 levels were measured in plasma of 48 patients HIV positive patients enrolled in aprepitant trial. 29 patients received medication (125, 250 or 375 mg per day), 19 received placebo for 14 days. Changes in IL-6 are shown as delta [IL-6] between baseline and after 2 weeks of treatment with aprepitant measured.

levels of innate immunity (LUNK and intra cellular IFNy in natural killer cells) and decreased levels of systemic inflammation (IL-6 and CRP).

C.3.2 Biostatistical Consideration and Analysis Plan

C.3.2.a Methods and Approach

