Primary Aims: For Primary Aims 1A and 1B, participants will provide measures of innate immunity (LUNK and intracellular IFN- γ) and inflammation (IL6 and CRP) at baseline, and at weeks 2, 4, and 10. The measures will be continuously distributed, and we will use linear mixed effects models, probably after log transformation of a response, to estimate the effects of medication group and time on the distribution of the responses across the 10 week period. The explanatory variables in these models will be a binary indicator of medication group, variables representing time effects, together with possible group by time interaction terms. Time will be modeled as a discrete factor. For the covariance structure, we expect that a random intercept model will provide a good fit to the data, and will also compare other possible specifications using BIC comparisons.

Secondary Aim: In the Secondary Aim, we will examine relationships between the effects of Escitalopram versus Placebo on depressive symptoms and the effects on the primary biological responses. Hamilton scores will be obtained at baseline and at weeks 2, 4, and 10.

First, we will examine whether participants showing improvement in depression measures are also those showing improvement in primary biological measures. Here, we will calculate change from baseline scores for the Hamilton and for the four immunity measures. For each immunity measure and Hamilton, we will use bivariate mixed effects models to simultaneously model the pattern of depression change scores and immunity change scores across weeks 2 through 10. Here, for each of the four immunity measures, we are modeling the three Hamilton change scores and the three immunity change scores as a six-dimensional response, with explanatory variables of week, medication, and type of response (depression versus immunity). Our hypotheses, that decreases in Hamilton will be associated with increases in innate immunity, and with decreases in inflammation, will be tested by modeling the covariance structure, and testing individual covariances for significant differences from zero. We will perform these analyses separately for the four immunity responses.

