Second, we will test whether Escitalopram has direct and indirect effects on the immune responses. The primary analyses (for Aims 1A and 1B) have addressed the total effect of Escitalopram on the four immunity measures. One set of analyses will use the confidence limit approach of MacKinnon et al (135, 136), to test whether changes in Hamilton score at week 2 (and, separately, at week 4) mediate the change in immunity measures at week 10. To obtain a complete picture of the possible mediation effects of depression, we will also perform these analyses using 50% reduction in HAM-D, and HAM-D ≤ 7 , as the measures of the direct effect of Escitalopram on depression. We will perform these analyses on the four innate immunity and inflammation responses separately. These mediation analyses focus on the end of treatment time point. To obtain information on longitudinal mediation across the full period, we will use latent growth curve mediation models (MacKinnon, 2008, 8.10-8.14). These models are similar to the bivariate mixed effects models described above, but here we include additional regression terms to isolate effects of depression on immunity across time, and random intercepts and slopes for the repeated depression scores and the repeated immunity scores, with the intercept and slope of the immunity response regressed on the intercept and slope of the depression response. MacKinnon (2008) describes how the estimated coefficients of these models can be used to provide estimates and confidence intervals for the indirect and direct effects of Escitalopram on immunity.

C.3.2.b Power Analysis and Sample Size Calculation for Primary Aims

We use two-sided hypothesis tests, and assume 10% loss to attrition over the 10 weeks. We set an overall alpha level of 5% within the innate immunity and inflammation hypotheses, so each Hypothesis is tested at alpha=0.025. We use the methods of Hedeker et al (122): assuming a within person correlation of 0.6 between visits, we have 80% power to detect a linear group by time effect (from week 0 through week 10) of Cohen's $d=0.40$ or higher, and 80% power to detect a main effect (from week 2 through week 10) of $d=0.4$ or higher.

C.3.3 Expected Outcomes, Potential Problems and Alternative Approaches

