Effects of patient characteristics: Differences in patient demographics (such as age and gender) and characteristics (such as depression severity, levels of life stress, social support, neurocognitive capacity, time since HIV diagnosis, endocrine status, and systemic inflammation level) could potentially moderate the effects of SSRI treatment on our primary outcomes. Some research has suggested that baseline levels of CRP (139), IL-6 and TNF- α (7, 86, 140, 141) and of other biological indicators (7, 86, 132) may influence the effects of

SSRI on depression. We will perform a series of moderator analyses (142) to address these questions. The potential moderators will be included as main effects and as interactions with group in the analyses described above for the primary responses. We will use multivariate analyses analogous to the univariate analyses to examine SSRI effects on a wider range of biological responses to include endocrine hormones (cortisol, ACTH, DHEA), as well as the flow cytometry panels noted above.

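### The primary mixed model uses neither baseline adjustment nor the randomisation strata; at the plan's correlation of 0.6, baseline adjustment alone would cut the variance by 49% (week 2–10 effect) or about 14% (linear group by time)

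*SAP*

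**What the plan says.** LUNK, intracellular IFN-γ, IL-6 and CRP are each measured at baseline and at weeks 2, 4 and 10. SAP C.3.2.a (Primary Aims) and the protocol's Accrual section specify a linear mixed model whose explanatory variables are "a binary indicator of medication group, variables representing time effects, together with possible group by time interaction terms". Time is a discrete factor, and for the covariance "we expect that a random intercept model will provide a good fit to the data".

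The power section (SAP C.3.2.b) refers to two effects: "80% power to detect a linear group by time effect (from week 0 through week 10") and "80% power to detect a main effect (from week 2 through week 10"). Aim 1B describes the inflammation endpoint differently: "propose to use changes in those two markers as a primary outcome of our study".

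The protocol's Randomization paragraph says: "Stratification based on race, sex, and baseline depression symptom severity, will be incorporated", with HAM-D of 20 or more marking the severe group. Patient characteristics enter an outcome model only in SAP C.4: "The potential moderators will be included as main effects and as interactions with group in the analyses described above for the primary responses". Those are moderator analyses. In SAP C.5, baseline characteristics enter only the dropout model used for sensitivity weights. Neither section changes the primary model.

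**The concern.** In a randomised trial the arms have the same expected baseline. A model that knows this, through a baseline covariate or a common baseline mean, removes the part of the follow-up variance that baseline predicts. The plan assumes a within-person correlation of 0.6, so that part is large.

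As powered, the week 2–10 effect makes no use of baseline. The linear effect from week 0 does use it, but lets the two arms have different baseline means. A change-from-baseline contrast, which the Aim 1B wording could imply, uses baseline inefficiently.

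What is at stake is the size of effect the trial can detect with the same participants and assays. The plan also does not say which contrast (level, change or trend) will be tested, so the precision obtained depends on a choice still open. Leaving the stratification factors out makes the test conservative to the extent that they predict the markers.

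**Working it through.** **Inputs.** 180 randomised (protocol, Randomization), half per arm (protocol, Potential Study Benefits), 10% attrition: 90 × 0.9 = 81 per arm. Two-sided alpha 0.025, correlation ρ = 0.6 (SAP C.3.2.b). A random intercept gives the same correlation between every pair of visits. Variances below are per participant, in units of SD².

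Detectable effect at 80% power: d = (2.2414 + 0.8416) × √(2 × variance / 81).

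**Reproducing the plan's figures.**
- Week 2–10 mean, no baseline: variance (1 + 2ρ)/3 = 0.7333, so d = 3.083 × √(2 × 0.7333/81) = 0.415. With 10% lost gradually from 90 per arm, d is 0.400 to 0.403. The protocol states 0.41 and the SAP 0.4.
- Linear group by time at weeks 0, 2, 4, 10 (time scaled to 0, 0.2, 0.4, 1; sum of squares about the mean 0.56), with a free baseline difference: (2/81) × 0.4/0.56 = 0.01764, so d = 3.083 × √0.01764 = 0.409. The SAP states 0.40 and the protocol 0.42.

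The stated power therefore matches an analysis without baseline adjustment.

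**Week 2–10 effect under three analyses.**

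| Analysis | Variance | Detectable d | Power at d = 0.41 |
|---|---|---|---|
| Unadjusted level | 0.733 | 0.415 | 79% |
| Change from baseline | 0.7333 + 1 − 1.2 = 0.533 | 0.354 | 91% |
| Baseline-adjusted | 0.7333 − 0.6² = 0.373 | 0.296 | 98% |

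Adjustment saves 0.36/0.7333 = 49% of the variance (29% of the standard error) against the unadjusted level. Against change it saves 0.16/0.5333 = 30% (16% of the standard error). Keeping baseline as a response with a common mean gives the same 0.373 by generalised least squares.

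**Linear group by time.** A common baseline mean reduces 0.01764 to 0.01516, a ratio of 0.860, or 14%. Detectable d falls from 0.409 to 0.380, and power at the SAP's d = 0.40 rises from 78% to 84%. As a linear contrast in a fully discrete-time model (week weights −4, −2, 0, 6), the variance falls from 22.4 to 19.84, or 11%, and detectable d from 0.409 to 0.385.

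**Lower baseline correlation.** Assumption: post-baseline visits stay correlated at 0.6 and the baseline-to-follow-up correlation is r. The adjusted variance is 0.7333 − r² and the change variance 1.7333 − 2r.

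| r | Adjusted | Change | Saving against unadjusted | Power at d = 0.41: unadjusted / change / adjusted |
|---|---|---|---|---|
| 0.3 | 0.643 | 1.133 | 12% | 79 / 58 / 84% |
| 0.4 | 0.573 | 0.933 | 22% | 79 / 68 / 89% |
| 0.5 | 0.483 | 0.733 | 34% | 79 / 79 / 93% |

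Adjustment beats both alternatives throughout. Change scores are worse than no adjustment at 0.3 and 0.4.

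**Simulation check.** With 10,000 trials at r = 0.6 and d = 0.41, power was 77.9%, 89.7% and 97.5% (unadjusted, change, adjusted). Under the null all three rejected in 2.5–2.6% of trials, so type I error is unaffected.

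**Strata.** The documents do not say how strongly race, sex or severity predict the markers, so no gain is computed.

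**The case against.** The strongest reply is that 49% rests on the least favourable comparator. The week 2–10 level appears only in the power statement. The model itself has baseline among the responses, so its group-by-time terms are changes from baseline. Read that way, the saving is 30% for the week 2–10 mean, and 11% to 14% for a linear trend. This is fair as far as it goes: the percentage depends on the contrast, and the plan does not fix one. A contrast purely among weeks 2, 4 and 10 would gain nothing, since the variance of the week 10 minus week 2 difference is 0.8 either way. But 49% and 14% belong to the two effects the plan itself powers, and the unadjusted level is what reproduces its figures.

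Having baseline among the responses does not by itself recover the efficiency; that takes adjustment or the common-mean constraint. If the optional interaction were dropped and one group effect fitted over all four visits, a post-baseline effect of 0.41 would be diluted to 0.41 × 3/4 = 0.31.

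Three further points stand as limits. The 0.6 is a planning value, and no observed correlation is given for any marker. Nothing shows that the strata predict the markers. And this is a valid analysis that roughly delivers its planned power. A baseline covariate would also drop participants without a baseline assay, but the common-mean version keeps them.

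**Conclusion.** The concern holds as a loss of efficiency. There is no bias, no inflation of type I error and no material error in the stated power.

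At the plan's correlation of 0.6 with a random intercept, baseline adjustment saves 49% of the variance for the week 2–10 effect as powered, 30% if that effect is analysed as change, and 11–14% for the linear test on actual weeks. For the week 2–10 effect, 81 × 0.3733/0.7333 ≈ 41 adjusted participants per arm would carry the information of 81 unadjusted. If baseline correlates with follow-up at only 0.3, the saving on that effect is 12%.

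All these figures come from baseline adjustment alone. Including the strata follows from the design, but its gain is unknown. The change should be made; the trial's validity does not depend on it.

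**What to change.** In SAP C.3.2.a and the matching protocol text, specify one of the following for each of the four markers:

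- Model the (log) values at weeks 2, 4 and 10 on group, visit, group by visit, baseline (log) value by visit, and the stratification factors (race, sex, HAM-D of 20 or more).
- Keep baseline as a response, with a common baseline mean across arms, group-by-visit terms after baseline, and the same stratification factors. This version retains participants who lack a baseline assay.

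Then name the treatment contrast to be taken from that model, either the week 2–10 average or the linear trend from week 0, and apply the same rule to all four markers.

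The cost is SAP and protocol wording and a few degrees of freedom; every variable is already collected. Because participants are unblinded at their week 10 visit, the revised model should be dated and fixed before anyone examines marker results by arm.

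### The primary covariance is expected to be a random intercept and is settled by BIC among unlisted rivals; if correlation fades over the visits, single-contrast error rates can be wrong in either direction

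*SAP*

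**What the plan says.** SAP C.3.2.a (Primary Aims) has LUNK, intracellular IFN-γ, IL-6 and CRP measured "at baseline, and at weeks 2, 4, and 10". Each is analysed with a linear mixed model. On the mean structure: "Time will be modeled as a discrete factor", and the explanatory variables are medication group with "variables representing time effects, together with possible group by time interaction terms". On the covariance: "we expect that a random intercept model will provide a good fit to the data", and the authors "will also compare other possible specifications using BIC comparisons". The Protocol's Accrual section repeats this text.

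The rival structures are not listed. There is no fallback and no sandwich variance. The sensitivity analyses in SAP C.5 deal with dropout and non-adherence, not with the covariance.

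SAP C.3.2.b sets the error rate: "We set an overall alpha level of 5% within the innate immunity and inflammation hypotheses, so each Hypothesis is tested at alpha=0.025". It powers two effects, a linear group-by-time effect over weeks 0 to 10 and a main effect over weeks 2 to 10, using a single within-person correlation of 0.6. No section names one contrast as the primary test.

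**The concern.** A random intercept with equal residual variance forces the correlation between baseline and week 2 to equal that between baseline and week 10. The gaps between visits are 2, 2 and 6 weeks, so a biomarker whose correlation weakens with time would break that assumption. The model would then use one average correlation for every contrast. Contrasts between distant visits would get standard errors that are too small, and contrasts between neighbouring visits would get standard errors that are too large.

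BIC is the only safeguard in the plan. An unstructured matrix for four visits has 10 parameters against 2 for the random intercept. With 162 subjects its extra BIC penalty is 8 × ln(162) = 8 × 5.088 = 40.7, so a moderate departure may not displace the random intercept. A random intercept plus slope has 4 parameters and pays only 2 × 5.088 = 10.2. How well BIC protects the test therefore depends on which rivals are entered, and the plan does not say.

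**Working it through.** **Inputs from the documents.** 180 subjects, half to each arm (Protocol, Randomization and Potential Study Benefits); visits at weeks 0, 2, 4 and 10; two-sided alpha 0.025; 10% attrition; correlation 0.6 (SAP C.3.2.b).

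**Assumptions.** Equal variances over time, complete data and 81 per arm (90 less 10%). The fade is assumed, so a range is shown.

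**Step 1: the plan's own figure.** z(0.9875) + z(0.80) = 2.241 + 0.842 = 3.083. Under constant correlation 0.6:

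- Main effect, weeks 2-10: d = 3.083 × √[(2/n)(1 + 2×0.6)/3].
- Linear effect as the 0-to-10-week difference: d = 10 × 3.083 × √[(2/n)(1 − 0.6)/56], where 56 is the sum of squares of the centred weeks (−4, −2, 0, 6).

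| n per arm | Main | Linear |
|---|---|---|
| 90 | 0.394 | 0.388 |
| 85.5 (half the attrition) | 0.404 | 0.399 |
| 81 (full attrition) | 0.415 | 0.409 |

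The SAP's 0.40 for both effects reproduces at 85.5 per arm. The Protocol's 0.42 (linear) and 0.41 (main) are close to the 81-per-arm row. The stated power thus rests on the same constant correlation that a random intercept implies.

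**Step 2: random intercept kept, correlation fading.** With equal variances the model uses the mean r̄ of the six pairwise correlations. For contrast c the standard-error ratio is k = √(c′V̄c / c′Rc), where V̄ is the constant-correlation matrix and R the true one. The actual alpha is 2Φ(−2.241k). For the change to week w, k = √[(1 − r̄)/(1 − ρ(0,w))].

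Three assumed patterns:

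- A: 0.65, 0.58 and 0.49 with baseline; 0.65 (weeks 2-4), 0.51 (2-10), 0.54 (4-10); r̄ = 0.570.
- B: linear in lag from 0.66 (2 weeks) to 0.50 (10 weeks); r̄ = 0.593.
- C: linear in lag from 0.70 to 0.45; r̄ = 0.596.

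Example, week-10 change under C: k = √(0.404/0.55) = 0.857, and alpha = 2Φ(−1.921) = 0.055. Linear effect under C: c′Rc = 33.3 against 56 × 0.404 = 22.6, so k = 0.824 and alpha = 0.065.

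| Test (nominal 0.025) | A | B | C |
|---|---|---|---|
| Week-10 change | 0.040 | 0.043 | 0.055 |
| Linear group by time | 0.047 | 0.049 | 0.065 |
| Week-4 change | 0.023 | 0.020 | 0.018 |
| Week-2 change | 0.013 | 0.014 | 0.009 |
| Main effect, weeks 2-10 | 0.025 | 0.025 | 0.025 |
| Joint 3-df interaction | 0.027 | 0.027 | 0.030 |

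The joint row is the large-sample tail of the weighted chi-square. The main effect holds because the mean correlation among weeks 2, 4 and 10 is almost exactly r̄: under B, (0.66 + 0.54 + 0.58)/3 = 0.593.

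**Step 3: adding the BIC step.** For 300 simulated covariance matrices per pattern, the candidates were fitted and BIC (using the number of subjects) chose among them. Cells show how often the random intercept was kept, then alpha for the week-10 change.

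| Rivals to the random intercept | B | C |
|---|---|---|
| Unstructured only | 98%, 0.044 | 66%, 0.045 |
| AR(1), unstructured | 91%, 0.041 | 42%, 0.032 |
| Random intercept plus slope | 41%, 0.031 | 5%, 0.026 |
| Broad set | 21%, 0.032 | 1%, 0.030 |
| *Unstructured fixed in advance* | *0.027* | *0.027* |

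With 300 draws a retention percentage has a standard error of at most √(0.25/300) = 2.9 points.

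A separate simulation of 6,000 trials under A, with random slope and unstructured as rivals, kept the random intercept in 50% of trials. For the week-10 change it gave 0.041 (random intercept), 0.031 (BIC-chosen) and 0.027 (unstructured). For the linear effect it gave 0.048, 0.035 and 0.025.

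**Step 4: the two ends.** Under strong fade (0.75 to 0.35, or exponential decay averaging 0.6) BIC rejects the random intercept in essentially every draw, and alpha for the week-10 change is 0.021 to 0.027. Under constant 0.6 the random intercept and unstructured models agree (about 0.025 and 0.026).

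**The case against.** The strongest reply is that the documents never make the baseline-to-week-10 change the primary test. That is right. Week-10 change appears as an outcome only in the secondary mediation analysis. With time as a factor the natural interaction test is the joint 3-df one, and both it and the powered main effect stay near nominal even with the random intercept kept. A reader might infer that the plan's group-by-time p-values are in general too small; the calculations do not support that, since some contrasts become conservative. What remains is that SAP C.3.2.b powers the linear group-by-time effect, which is the contrast hit hardest, and that SAP Aim 1B describes changes in IL-6 and CRP as a primary outcome.

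A second reply is that BIC is itself the correction. Under strong fade it is. Under mild to moderate fade the protection depends on an unspecified candidate list.

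Third, a reader might infer that the model is picked to suit the result. The text does not support this: the expected structure and the criterion are stated in advance, and BIC does not look at the treatment p-value. The gap is only that the candidates are open.

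Fourth, nothing in the documents shows that these four markers lose correlation over 10 weeks. This stands, and it is why a range is given.

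**Conclusion.** The point holds as a cheap improvement, not as a demonstrated inflation of the trial's error rate. The plan expects a covariance that ignores the spacing of the visits, leaves its replacement to BIC over unnamed rivals, and names no robust variance. If correlation fades mildly to moderately and the random intercept is kept, nominal 0.025 becomes about 0.040 to 0.055 for the week-10 change and 0.047 to 0.065 for the linear group-by-time effect. It falls to 0.009 to 0.014 for the week-2 change and 0.018 to 0.023 for the week-4 change. With the BIC step included, the week-10 figure runs from close to nominal to about 0.045. The weeks 2-10 main effect and the joint interaction test are nearly unaffected.

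These sizes rest on assumed fade patterns, equal variances over time, complete data and 81 per arm. If the correlation really is constant at 0.6, nothing is lost under the plan as it stands.

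**What to change.** In SAP C.3.2.a and the matching Protocol text:

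- For the primary tests, pre-specify an unstructured covariance over the four visits, with Kenward-Roger degrees of freedom.
- If that model does not converge, use a random intercept with sandwich standard errors.
- Drop the BIC selection for the primary tests.
- Name the primary contrast for each marker, since exposure to this problem depends on which one is tested.

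The cost is SAP wording and eight more covariance parameters (10 against 2). With 180 subjects the loss of precision is negligible: under constant correlation the two models give about 0.025 and 0.026 for the week-10 change. Sample size, visits and procedures do not change.

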Recruitment Procedures The enrollment of 180 depressed HIV positive, cART suppressed individuals will be accomplished through the implementation of a series of structured and well-coordinated recruitment and screening activities. These activities include: 1) the use of the Penn CFAR HIV clinical registry; 2) traditional advertising via fliers and print media; 3) networking with MH and HIV clinicians, clinic staff, case managers and patients; and 4) regular presence at clinic staff meetings to provide project visibility and feedback on project enrollment. We will post the IRB approved flyers in key locations and on the PMHARC HIV Research Bulletin Board, a web site that provides a central location for posting IRB recruitment flyers. We will begin recruitment by targeting the five adult HIV clinics that operate under the umbrella of the University of Pennsylvania Health System (UPHS). The UPHS clinics serve approximately 2,000 patients each year and are linked administratively, share a common database and electronic medical record system. We will also recruit participants from the Drexel Partnership Clinic, the Temple HIV Clinic and the Lax Clinic of Philadelphia Fight. Thus, collectively the clinics from which we will be recruiting see approximately 7,500 patients each year. Recruitment will be initiated upon notice of grant award and enrollment will begin in the fourth month of the study and continue for 53 months. **Power Analysis and Sample Size Calculation for Primary Aims** We used two-sided hypothesis tests, and assumed 10% loss to attrition over the 10 weeks. We set an overall alpha level of 5% within the innate immunity and inflammation hypotheses, so each Hypothesis is tested at $\alpha=0.025$. We used the methods of Hedeker et al. (152): assuming a within person correlation of 0.6 between visits, we have 80% power to detect a linear group by time effect (from week 0 through week 10) of Cohens $d=0.42$ or higher, and 80% power to detect a main effect (from week 2 through week 10) of $d=0.41$ or higher. **Biostatistical Consideration and Analysis Plan for Primary Aims** For Primary Aims 1A and 1B, participants will provide measures of innate immunity and inflammation at baseline, and at weeks 2, 4, and 10. The measures will be continuously distributed, and we will use linear mixed effects models, probably after log transformation of a response, to estimate the effects of medication group and time on the distribution of the responses across the 10 week period. The explanatory variables in these models will be a binary indicator of medication group, variables representing time effects, together with possible group by time interaction terms. Time will be modeled as a discrete factor. For the covariance structure, we expect that a random intercept model will provide a good fit to the data, and will also compare other possible specifications using BIC comparisons. **Biostatistical Consideration and Analysis Plan for Secondary Aim First**, we will examine whether participants showing improvement in depression measures are also those showing improvement in primary biological measures. Here, we will calculate change from baseline scores for the HAM-D and for the four immunity measures. For each immunity measure and HAM-D, we will use bivariate mixed

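### From the same stated inputs the SAP gives a detectable linear effect of d = 0.40 and the protocol 0.42, and neither says how the 10% loss enters

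*SAP*

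**What the plan says.** SAP section C.3.2.b and the power paragraph in the protocol's Accrual section are worded almost alike. On sidedness and loss, the SAP says "We use two-sided hypothesis tests, and assume 10% loss to attrition over the 10 weeks" and the protocol says "We used two-sided hypothesis tests, and assumed 10% loss to attrition over the 10 weeks". Both split a 5% alpha in two; in the SAP's words, "so each Hypothesis is tested at alpha=0.025". Both rely on "assuming a within person correlation of 0.6 between visits" and both cite a published method for the calculation.

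The results differ. For the linear effect the SAP gives d = 0.40, and the protocol gives a "linear group by time effect (from week 0 through week 10) of Cohens $d=0.42$ or higher". For the main effect the SAP has "80% power to detect a main effect (from week 2 through week 10) of $d=0.4$ or higher" and the protocol has "80% power to detect a main effect (from week 2 through week 10) of $d=0.41$ or higher".

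Neither power paragraph gives a number per arm or says how the loss is applied. The figure of 180 subjects comes from the protocol (Accrual, Randomization) and from the sample-repository text in SAP section C.4. Equal allocation follows from the protocol's Potential Study Benefits section. The protocol also says, at the end of the Accrual section and under Treatment, that withdrawn subjects are replaced.

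**The concern.** The detectable effect is the only quantitative justification that either document gives for 180 subjects. One set of inputs and one formula should give one answer. The main-effect figures could agree, because the SAP prints 0.4 to one decimal and the protocol's 0.41 rounds to it. The linear figures cannot be reconciled in that way. The SAP is dated March 2015 and the protocol February 2021, but none of the listed inputs changed in between, so the later date does not explain the new result. A reader cannot tell which figure supports the sample size.

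**Working it through.** **Inputs from the documents.** Two-sided alpha 0.025, power 80%, correlation 0.6, 10% loss, 180 subjects in two equal arms (90 per arm), and visits at weeks 0, 2, 4 and 10 (SAP C.3.2.a).

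**Assumptions added here.** Compound symmetry with unit variance at each visit. The main effect is the group difference averaged over weeks 2, 4 and 10. The linear effect is the slope difference multiplied by 10 weeks.

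The multiplier is 2.241 + 0.842 = 3.083. Detectable d is 3.083 × SE. Power at d is Φ(d/SE − 2.241).

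**Flat loss: 10% missing at every visit, so 0.9 × 90 = 81 per arm**
- Main: SE = √(2 × [(1 + 2 × 0.6)/3] / 81) = 0.1346, so d = 0.415. This is close to the protocol's 0.41, at which power is 79.0%.
- Linear: the squared deviations of 0, 2, 4, 10 from their mean of 4 sum to 16 + 4 + 0 + 36 = 56. SE = 10 × √(2 × 0.4 / (81 × 56)) = 0.1328, so d = 0.409.

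**Gradual loss: 98%, 96% and 90% retained at weeks 2, 4 and 10 (assumed), all observed visits used**
- The last visit is week 10 for 90% of subjects, week 4 for 6%, week 2 for 2% and baseline for 2%.
- Main: a subject with k post-baseline visits contributes information k/(1 + 0.6(k − 1)), which is 1, 1.25 and 1.364 for k = 1, 2 and 3. The average is 0.02 × 1 + 0.06 × 1.25 + 0.90 × 1.364 = 1.322. SE = √(2 / (90 × 1.322)) = 0.1296, so d = 0.400. This reproduces the SAP's main-effect figure.
- Linear: averaging the generalised least squares information for intercept and slope over the same patterns gives 1.4125 (intercept), 5.3315 (cross term) and 148.224 (slope). Slope information is 148.224 − 5.3315²/1.4125 = 128.10, against 56/0.4 = 140 for a complete subject. SE = 10 × √(2 / (90 × 128.10)) = 0.1317, so d = 0.406.

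| Loss | Linear d | Power at 0.40 | Main d | Power at 0.40 |
|---|---|---|---|---|
| None (90 per arm) | 0.388 | 82.5% | 0.394 | 81.4% |
| Flat (81 per arm) | 0.409 | 78.0% | 0.415 | 76.8% |
| Gradual | 0.406 | 78.7% | 0.400 | 80.1% |

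**Sensitivity of the linear figure.** Treating visits as equally spaced gives 0.411 (flat) and 0.404 (gradual). A t-based calculation with flat loss gives 0.413 to 0.414. A contrast formula using the number seen at each visit, with loss spread evenly by week, gives 0.401 to 0.403 (and 0.405 for the main effect). So with a total loss of 10%, the SAP's 0.40 lies at the favourable edge of the results and the protocol's 0.42 lies above all of them. At d = 0.42 linear power is about 82% with flat loss.

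**The case against.** A reader might infer that the SAP's 0.40 is not delivered once the 10% loss is applied. The documents do not support that in general. It holds clearly only if the whole 10% is absent from every visit, and neither document says so. Both describe loss over the 10 weeks, and SAP section C.5 says that the mixed models use whatever data subjects provide, so a dropout's earlier visits count. On that reading the main effect has 80.1% power at 0.40 and the linear effect 78.7 to 79.2%. Replacement of withdrawn subjects would weaken the flat-loss reading further.

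There is some support on the other side. C.5 ties the use of all available data to one hypothesis of Aim 1, and says that for the other primary responses dropouts contribute nothing. That resembles 81 per arm. It is hard to square with C.3.2.a, where all four measures are taken at weeks 2, 4 and 10, so it does not settle the matter.

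It is also fair to say that the inputs are shown to be the same only as far as they are stated. The handling of attrition could differ, and the authors' formula cannot be confirmed: the SAP's reference 122 is listed as a paper on a thresholds-of-change model. The formulas used here put the linear figure below the main one at 81 per arm, whereas the protocol has the reverse order, so they may not be the authors' own. These points limit confidence in any single replacement value. They do not remove the conflict between 0.40 and 0.42.

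**Conclusion.** The inconsistency in the linear effect is real: 0.40 and 0.42 are both given at 80% power from the same listed inputs, so at least one is wrong as written. The main-effect figures, 0.4 and 0.41, may differ only by rounding.

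The size is small: 0.02 in d between the documents, and at most about 3 points of power at d = 0.40 (76.8% against 80%) in the least favourable case. The protocol's linear 0.42 is slightly conservative. This is a minor reporting correction and no ground for calling the trial underpowered. The recalculated values rest on compound symmetry, equal arms, the definitions of d given above, and, for gradual loss, an assumed retention pattern.

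**What to change.** State one pair of detectable effects in both documents, to two decimals, with the number per arm, the formula, how the 10% loss is applied, and whether replacement of withdrawn subjects is counted. On the calculation above, the pair depends on the attrition handling:

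- Flat loss, 81 evaluable per arm: 0.41 (linear) and 0.42 (main, 0.415 rounded up).
- Gradual loss with all observed data used: 0.41 (linear, 0.406 with the actual visit weeks) and 0.40 (main), with the assumed retention at each visit stated.

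If the authors' own formula gives other values, print those and show the formula. The cost is a change of wording in two documents and a slightly less favourable figure in the SAP. No extra patients are needed.
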